1.2.1. Analysis Timepoints

Following the study premature termination by the sponsor, the final analysis will be performed at the final database lock only, when all participants have completed the safety follow-up phone call or discontinued prematurely.

1.2.2. DMC and Steering Committee

A sponsor Data Monitoring Committee (DMC) and a Steering Committee will be established.

The sponsor DMC (internal) has the overall responsibility for safeguarding the interests of participants and will review on regular basis the results of safety analyses performed by an unblinded statistical support group (SSG) independent from the study team. The DMC will provide recommendations to the study team. The committee is governed by a dedicated DMC charter.

A Steering Committee is involved in the study design and will provide guidance on the study conduct and study publications. The committee is governed by a dedicated Steering Committee charter.

1.2.3. Randomization and blinding

Treatment Allocation

Procedures for Randomization and Stratification

Central randomization will be implemented in this study. Participants will be randomly assigned to 1 of 2 treatment groups based on a computer-generated randomization schedule prepared before the study under the supervision of the sponsor. The randomization will be stratified by PH-specific therapy at baseline (yes vs no). The Interactive Web Response System (IWRS) will assign a unique treatment code, which will dictate the treatment assignment and matching study treatment kit for the participant. The requestor must use his or her own user identification and personal identification number when contacting the IWRS and will then give the relevant participant details to uniquely identify the participant.

Blinding

The study period up to EOMOP will be performed in a DB fashion. Unblinding will occur after all patients completed EOMOP.

The investigator will not be provided with randomization codes. The codes will be maintained within the IWRS, which has the functionality to allow the investigator to break the blind for an individual participant.

Under normal circumstances, the investigator and study personnel, the participants, sponsor personnel, and CRO personnel involved in the conduct of the study will remain blinded to the study treatment until EOMOP analysis timepoint, or until the study is stopped prematurely. In order to preserve the blind of each individual participant until EOMOP analysis timepoint, randomization codes and, if required, the translation of randomization codes into treatment and

control groups will be disclosed to those authorized and only for those participants included in the analyses for the DMC. An internal SSG will conduct the analyses and present unblinded results to the DMC (see specific DMC charter).

The investigator may in an emergency determine the identity of the treatment by contacting the IWRS. While the responsibility to break the treatment code in emergency situations resides solely with the investigator, it is recommended that the investigator contact the sponsor or its designee if possible to discuss the particular situation, before breaking the blind. Telephone contact with the sponsor or its designee will be available 24 hours per day, 7 days per week. In the event the blind is broken, the sponsor must be informed as soon as possible. The date, time, and reason for the unblinding must be documented in the Investigator Site file and in the appropriate section of the eCRF, and in the source document. The documentation received from the IWRS indicating the code break must be retained with the participant's source documents in a secure manner.

If a suspected unexpected serious adverse reaction (SUSAR) occurs for a participant in the study, unblinded SUSAR information will be provided to DMC and respective health authorities and Independent Ethics Committees (IECs) or Institutional Review Boards (IRBs) only. SUSARs will be reported to investigators in a blinded fashion. The treatment assignment will not be communicated to site personnel or to sponsor study team.

Participants who have had their treatment assignment unblinded may stay on study treatment after unblinding provided the following conditions are met: emergency unblinding for accidental or intentional overdose or medication error.

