3.0	01 December 2022	Update the SAP for a synoptic CSR	Update after announcement of study termination by the Sponsor (26 Sep 2022). Reporting simplified. All listings are kept, and all the analyses already planned and produced for DMC.

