- A DB extension period extending intervention for participants who do not prematurely discontinue study intervention before EOMOP: The period starts in the evening of the day of the EOMOP visit and ends with the end-of-treatment (EOT) visit. This period will last approximately 5 months. All participants entering the DB extension period will continue taking blinded study intervention (selexipag or placebo) during this period. Study intervention allocation will be unblinded approximately 1 month before the expected EOT visit.
- A safety follow-up period starting on the day after the last dose of study intervention and ending with the safety follow-up call at the End-of-Study (EOS) visit. For an individual participant, EOS visit is defined as follows:
 - For participants who complete the treatment, EOS visit is defined as the safety follow-up visit (TC) 30 (+5) days after last dose of study intervention.
 - For participants who prematurely discontinue study intervention for any reason before EOMOP visit (except for withdrawal from the study) but complete the main observation period, EOS visit corresponds to the last visit, which is either the EOMOP visit or the safety follow-up TC, whichever occurs last.
 - For participants who prematurely discontinue study intervention for any reason before the EOMOP visit and who decline to continue with visits and assessments up to the EOMOP visit, but agree to the collection of long-term survival information, the EOS visit corresponds to the last visit or TC before study discontinuation.
 - For participants who prematurely discontinue study intervention between the EOMOP and EOT visits for any reason (except for withdrawal from the study), the EOS visit corresponds to the safety follow-up TC.
 - For participants who complete the treatment and who are entering a continued access program (ie, other open-label extension study or post-trial access), the EOS visit is defined as the EOT visit and enrollment in the continued access program must occur on the day of the last visit in the SPHINX study.

Following the study premature termination by the sponsor, the EOMOP will refer to a premature EOMOP.

See figure below for the study design schematic overview.

EOMOP = end-of-main-observation-period; EOS = end-of-study; EOT = end-of-treatment; iMTD = individual maximum tolerated dose; TC = telephone call, V = visit; W = week.

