5.6.2. Adverse Events

The verbatim terms used in the CRF by investigators to identify adverse events will be coded using the Medical Dictionary for Regulatory Activities (MedDRA). Any AE occurring at or after the initial administration of study intervention through the day of last dose plus 3 days is considered to be treatment emergent. If the event occurs on the day of the initial administration of study intervention, and either event time or time of administration are missing, then the event will be

assumed to be treatment emergent. If the event date is recorded as partial or completely missing, then the event will be considered to be treatment emergent unless it is known to be prior to the first administration of study intervention based on partial onset date or resolution date. All reported treatment-emergent adverse events will be included in the analysis. For each adverse event, the number and percentage of participants who experience at least 1 occurrence of the given event will be summarized by intervention group.

Summaries will be displayed by treatment (selexipag or placebo) and will include all events up to 3 days after the last dose of study drug or EOS, whichever occurs first.

Summary tables will be provided for treatment-emergent adverse events:

- AEs
- Serious AEs (SAEs)
- AEs leading to discontinuation of study intervention
- AEs by severity
- AEs by relationship to study intervention
- All SAEs up to 30 days after the last study treatment

In addition to the summary tables, listings will be provided for participants who:

- Had AEs
- Had SAEs
- Had AEs leading to discontinuation of study intervention
- Had AEs of COVID-19
- AEs of special interest ([Appendix 8](#))

Deaths will be displayed by actual intervention received. Frequencies for the following parameters will be included in the summary table:

- Number of participants who died
- Cause of death
- Relationship to study intervention (yes/no)

A listing of participants who died will be provided.

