6.4. Appendix 4 Protocol Deviations

In general, the following list of major protocol deviations may have the potential to impact participants' rights, safety or well-being, or the integrity and/or result of the clinical study.

Participants with major protocol deviations will be identified prior to database lock and the participants with major protocol deviations will be displayed by category.

- Developed withdrawal criteria but not withdrawn
- Entered but did not satisfy criteria
- Received a disallowed concomitant treatment
- Received wrong treatment or incorrect dose
- Other

See TV-FRM-04718 "Major Protocol Deviation Criteria" for detailed definitions of major protocol deviations.

A separate listing for all protocol deviations related to COVID-19 will be also produced.

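### SAP v3.0 still ties the end of blinding to EOMOP, so the study team may be unblinded before the only remaining database lock

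*SAP*

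**What the plan says.** SAP section 1.2.3 has two sentences on when blinding ends. One reads "Unblinding will occur after all patients completed EOMOP". The other says that the investigator, study personnel, participants, sponsor personnel and CRO personnel "will remain blinded to the study treatment until EOMOP analysis timepoint, or until the study is stopped prematurely". Section 1.2 adds that, after termination, "the EOMOP will refer to a premature EOMOP".

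Section 1.2.1 now provides for one analysis: "the final analysis will be performed at the final database lock only, when all participants have completed the safety follow-up phone call", or have discontinued prematurely. For participants who complete treatment, "EOS visit is defined as the safety follow-up visit (TC) 30 (+5) days after last dose of study intervention".

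Two items of later work depend on this order. In SAP Appendix 4, "Participants with major protocol deviations will be identified prior to database lock"; nothing says this must come before unblinding. In SAP section 5.6.2 one planned table is "All SAEs up to 30 days after the last study treatment".

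The protocol's order was different. Its Synopsis and section 4.1 unblind the study team once the main observation period database has been locked. Section 6.3 allows potentially unblinding data to be kept from view until after the lock.

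**The concern.** SAP v3.0 was rewritten for a study that was being terminated. It dropped the EOMOP analysis and its lock but kept blinding text built around them. One trigger for ending the blind now refers to an analysis that no longer exists. Another, premature stop, is the very situation this version was written for. The third is completion of EOMOP, which can precede the only lock.

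Safety tables are most of what is still summarised by arm. Several rest on judgement: severity, relationship to study intervention, SAEs up to 30 days after last treatment, and cause and relatedness of deaths. If queries on these items are raised or resolved by people who know allocation, a reader of the report cannot tell which assessments were made or changed blind. The same applies to deciding which deviations count as major.

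**Working it through.** No error rate or sample size bears on this point, so the check is of the order of events.

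**Protocol and SAP side by side**

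| Item | Protocol (Amendment 3) | SAP v3.0 |
|---|---|---|
| Locks and analyses | Main-period lock and analysis, then a follow-up analysis at end of study (1.1, 4.1) | One final lock, one analysis (1.2.1) |
| Study-team unblinding | After the main-period lock (1.1, 4.1) | After EOMOP, at an EOMOP analysis timepoint, or on premature stop (1.2.3) |
| Safety data | Extension-period safety data reported separately at the second timepoint | Entire study period only (5.6) |
| Declared as a change? | Not applicable | Not mentioned in Appendix 2 |

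In the protocol, main-period data were locked before the team was unblinded. In SAP v3.0 no portion of the data is locked first, and assessments made before and after any unblinding would be pooled.

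**Length of the window under the EOMOP sentence**

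Let T be the day the last participant completes the premature EOMOP visit, d a participant's last-dose day, and L the final lock.

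- Unblinding is permitted from T.
- The safety call falls between d + 30 and d + 35.
- The call certainly falls after T if d + 30 > T, that is, if d is later than T − 30. It has certainly taken place by T if d + 35 ≤ T, that is, if d is T − 35 or earlier.
- For someone whose last dose is on day T, the call falls between T + 30 and T + 35. The window from T to L is then at least 30 days plus cleaning time.
- If everyone stopped dosing by T − 35, only cleaning time and deviation classification remain in the window.

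The SAP does not give last-dose dates relative to premature EOMOP, so T − d is an assumption and the result is a range.

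**Which safety outputs are exposed**

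Treatment-emergent AEs end at last dose plus 3 days (5.6.2). If dosing stops at or before T, new AEs entering the severity and relationship tables after T can have onset no later than T + 3. Earlier entries can still be queried and changed until L. The 30-day SAE table extends further, to d + 30.

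**Premature-stop clause**

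The version history dates the termination 26 Sep 2022 and SAP v3.0 01 December 2022: 4 + 31 + 30 + 1 = 66 days. Read literally, this trigger could have been met before v3.0 was approved.

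**The case against.** The strongest reply is that the protocol already covers this. The SAP is written against Amendment 3, which puts study-team unblinding after a lock. Appendix 2 announces no change to that, and only one lock remains. The EOMOP sentence sets an earliest time, so waiting for the final lock complies with it. All of this is true, but nothing in the SAP requires the wait, and the protocol rule names a main-period lock that no longer takes place.

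Several stronger readings are tempting and are not supported:

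- **The blind was lifted on 26 Sep 2022.** That is the date of the decision or announcement. The SAP still foresees premature EOMOP visits and follow-up calls after it. The premature-stop clause is also carried over from protocol section 6.3 and is not new.
- **Every SAE after last dose is exposed.** Participants who stopped 35 or more days before T had passed their call while the EOMOP sentence still kept the blind.
- **Deviation decisions could alter the results.** Deviations are only displayed by category, and SAP section 4 has no per-protocol set, so they exclude nobody.
- **Telling sites the allocation after EOMOP is itself a defect.** Protocol section 4.1 and SAP section 1.2 always planned release to sites about 1 month before EOT, and protocol section 4.2 gives informed decisions on post-study therapy as the reason. What is new is the loss of the lock that came before study-team unblinding.

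**Conclusion.** The point holds as a statement of what the text permits. SAP section 1.2.3 allows the study team and the sponsor and CRO personnel to be unblinded before cleaning, late SAE assessment and deviation classification are complete, and it loses the protocol's order of locking first.

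The size is modest. SAP section 2 tests no hypothesis and lists efficacy only, safety output is descriptive, and section 5.5.16 describes the number of participants as very limited. What is at stake is the credibility of those summaries, mainly post-dose SAEs, query resolution and deviation classification. No error rate is affected. A reader might infer that late data were in fact handled unblinded; the documents contain no evidence of that.

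The conclusion assumes that section 1.2.3 is applied as written and that some cleaning or follow-up remained after the last EOMOP visit. Because the lock must wait for outstanding calls, the second assumption is likely, but its extent cannot be read from the documents.

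**What to change.** Replace the two sentences in SAP section 1.2.3 with a statement to this effect: the study team, and the sponsor and CRO personnel involved in study conduct, remain blinded until the final database lock, except for emergency unblinding and the SSG/DMC; major protocol deviations are finalised before unblinding. Remove the reference to the EOMOP analysis timepoint.

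New wording cannot restore a blind already lifted. If unblinding has occurred, add its date to the listing of unblinded participants already planned in SAP section 5.2, and record the departure in Appendix 2. Section 1.2.3 already requires date, time and reason for emergency code breaks, so for those no new data are needed.

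When sites receive allocation should be stated separately and reconciled with protocol sections 4.1 and 4.2 and SAP section 1.2. No rule is proposed here. One keyed to the safety follow-up call would not fit participants entering continued access, whose EOS is the EOT visit.

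The cost is SAP wording. The downside is that the study team sees allocation a few weeks later.

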2. STATISTICAL HYPOTHESES

The primary objective is: " To assess the effect of selexipag versus placebo on pulmonary vascular resistance (PVR) in participants with sarcoidosis associated pulmonary hypertension (SAPH) up to Week 26."

As the study is prematurely terminated, no formal hypothesis will be tested, and all efficacy parameters will be listed only.

3. SAMPLE SIZE DETERMINATION

In a clinical study with bosentan in participants with SAPH (BOSAPAH-1), the observed GM ratio for *PVR post to pre percent* (defined in Section 5.3.1) was around 0.7 in 35 participants with SAPH at Week 16 (bosentan vs placebo). It was also 0.7 in the NS-304/02 study in 35 participants with PAH at Week 17 (selexipag vs placebo, with CV of *PVR post to pre percent* 0.28 vs 0.08). In the CTEPH studies MERIT-1 (80 participants) and BENEFIT (157 participants) the observed CVs of *PVR post to pre percent* approached 0.4. The blinded interim estimate in 79 participants of the TRITON study gives a CV of 0.5.

Sample size is calculated based on the statistical requirements to detect a clinically relevant difference between the selexipag and placebo groups using a 1:1 randomization ratio, a two-sided Type I error of 5% and a Type II error of 10% (90% power).

The following assumptions were made:

- A ratio of the GM of Week 26 (or premature EOT) to Baseline PVR values equal to 0.70 ie, a 30% relative decrease (improvement) in GM as compared to placebo;
- A coefficient of variation of the ratio of 0.50;
- Normal distribution for the log_e-transformed ratio of Week 26 (or premature EOT) to baseline PVR values.

Based on the above assumptions, 74 participants are required to establish the superiority of selexipag vs placebo with 90% power to correctly reject a false null hypothesis in favor of the alternative hypothesis.

4. POPULATIONS (ANALYSIS SETS) FOR ANALYSIS

Analysis sets are detailed in the [Table 3](#) below:

Table 3 Overview of the Different Populations for Analyses

Population	Description
Screened Analysis Set (SCR)	All participants who were screened and received a participant identification number.
Randomized Set (RS)	All participants assigned to a study intervention.
Safety Analysis Set (SAS)	All participants who received at least one dose of study intervention. Participants will be analyzed according to the intervention they actually received.

All baseline characteristics and safety analyses will be performed on the SAS. Efficacy will be listed only using the RS.

5. STATISTICAL ANALYSES

5.1. General Considerations

Following the sponsor decision to prematurely terminate the study due to slow enrollment (decision on 26 Sep 2022), the reporting is simplified: all listings and all the analyses already planned and produced for the sponsor DMC are kept for the final CSR. For efficacy, all parameters will be listed only.

Statistical analysis will be done by the sponsor or delegated to a Contract Research Organization under the responsibility of the sponsor. Unblinded analyses for the sponsor DMC will be performed by an SSG independent from the study team to protect from unblinding.

5.1.1. Visit Windows

As participants do not always adhere to the protocol visit schedule, the following rules are applied to assign actual visits to analysis visits. Listed below are the visit windows and the target days for each visit. The period starts with the administration of the first dose of DB study treatment. The reference day is Study Day 1, which is the day of randomization. If a participant has 2 or more actual visits in one visit window, the visit closest to the target day will be used as the protocol visit for that visit window. The other additional visit(s) will not be used in the summaries or analyses,

but they can be used for determination of clinically important endpoints. If 2 actual visits are equidistant from the target day within a visit window, the later visit is used.

All assignments will be made in chronological order. Once a visit date is assigned to a visit window, it will no longer be used for a later time point except for the endpoint. Listed below (Table 4) are the visit windows and the target days for each visit defined in the protocol.

Table 4 Visit Windows for double-blind treatment period

Parameter	Scheduled Visit Number	Time Interval (label on output)	Time Interval (Day)*	Target Time Point (Day)
All parameters [§]	1	Screening	< 1	[-30 to -1]
	2	Baseline	<=1	1
RHC (including PVR) / DLco / Spirometry / Arterial blood gas	5	Week 26	2 to 280	183
All Other parameters	3	Week 12	2 to 112	85
	4	Week 20	113 to 161	141
	5	Week 26	162 to 228	183
	6	Week 39	229 to 364	274
	7	Week 65	365 to 546	456
	8	Week 91	547 to 728	638
	9	Week 117	729 to 910	820
	10	Week 143	911 to 1092	1002

§ RHC is collected only during the screening period, not at baseline. *Relative to Study Day 1; DLco = diffusing capacity for carbon monoxide; RHC = right heart catheterization.

It is likely that only few participants (or none) will have an assessment after visit 10 and therefore those data will not be used in summary statistics and will be listed only.

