- a. Participants who discontinue study intervention and have their premature EOT visit before the EOMOP visit will continue with visits and assessments until the EOMOP visit. If the premature EOT visit falls within the visit window of any other scheduled visit, these visits can be combined, and assessments will not be repeated.
- b. The EOMOP visit will have to be performed within  $\pm 1$  month of the planned Visit 6/Week 39 of the last participant and will be announced approximately 9 months in advance. For the last participant the EOMOP Visit will be Visit 6/Week 39. For all other participants, if the EOMOP visit falls within the visit window of any other scheduled visit, these visits can be combined, and assessments will not be repeated.
- c. Unscheduled visits may be performed at any time during the study. Assessments (other than reporting of AE/SAE and concomitant medication) are to be performed at the discretion of the investigator and are reported in the eCRF. An unscheduled visit must be performed for reasons outlined in Section 8. Footnote [d](#) indicates which assessments are mandatory in case an unscheduled visit is performed for reasons outlined in Section 8.
- d. In case an unscheduled visit is performed for reasons outlined in Section 8, this assessment must be performed and recorded in the eCRF.
- e. Only for participants who prematurely discontinue from study intervention and who disagree to continue to perform visits and assessments until EOMOP, survival information will be collected yearly (Section 8.2.2.2).
- f. A serum pregnancy test must be performed in case of a positive urine pregnancy test.
- g. Transferred electronically by an external service provider.
- h. Assessment not collected in eCRF.
- i. In case of premature discontinuation of study intervention before Visit 5/Week 26 it is recommended to perform a postbaseline RHC and within 3 days after last dose of study intervention and before initiation of new PH-specific therapies if possible.
- j. If the 6MWT and RHC are assessed on the same day the RHC should be performed after the 6MWT.
- k. ABG is only mandatory at the premature EOT in case of premature discontinuation before Visit 5/Week 26 and can be done during the RHC taking into account the restrictions provided in Section 8.3.6.
- l. This assessment can only be done at the premature EOT in case of premature discontinuation of study intervention before Visit 6/Week 39.

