5.6. Safety Analyses

All safety analyses will be based on the safety analysis set based on actual intervention received, unless otherwise specified. Analyses will be conducted for the entire study period only.

For all continuous safety variables, descriptive statistics by intervention group will include the N, mean, standard deviation, median, minimum, and maximum. Categorical variables will be summarized by intervention group using frequency counts and percentages.

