5.6.3.4. Other Safety Parameters

Descriptive statistics of values and changes from baseline in supplemental oxygen rate, DLCO, FVC and arterial blood gas will be summarized over time on the SAS by treatment group for the entire study period.

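### SAP Table 4 has no end-of-treatment visit, so a premature EOT assessment more than 7 days from a target day drops out of the by-visit safety summaries

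*SAP*

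**What the plan says.** **Windowing rule (SAP 5.1.1).** Where two or more visits share a window, "the visit closest to the target day will be used as the protocol visit for that visit window". For the others, "The other additional visit(s) will not be used in the summaries or analyses", with a qualification: "but they can be used for determination of clinically important endpoints". A visit date already assigned to a window is not reused: "it will no longer be used for a later time point except for the endpoint". That endpoint time point is not defined.

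**Table 4.** Its rows are Screening, Baseline and Weeks 12, 20, 26, 39, 65, 91, 117 and 143. RHC, DLco, spirometry and arterial blood gas (ABG) share one post-baseline window, labelled Week 26, from Day 2 to Day 280. There is no EOT or premature EOT row. The actigraphy windows in Table 5, by contrast, do include an EOT value.

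**Follow-up after stopping (Protocol 1.3.2).** The premature EOT visit takes place within 7 days after the last dose. Footnote a says that participants who stop drug and "have their premature EOT visit before the EOMOP visit will continue with visits and assessments until the EOMOP visit". Sites may merge a premature EOT visit with a scheduled visit whose window it falls in.

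**Summaries kept in SAP version 3.0.** Section 5.6 states: "Analyses will be conducted for the entire study period only". Laboratory tests and vital signs are summarized by time point (5.6.3.1, 5.6.3.2). In 5.6.3.4, "Descriptive statistics of values and changes from baseline in supplemental oxygen rate, DLCO, FVC and arterial blood gas will be summarized over time". The limit of last dose plus 3 days in 5.6.2 applies to adverse events only.

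**The concern.** The assessment closest to the moment a participant stops drug is among the more informative safety observations, particularly if the stop was for intolerance. Table 4 gives it no place of its own. It must compete for a scheduled-week label, and the competitor is a visit planned to fall close to the target day. The summary row then shows either an off-drug value taken later or a value taken before the stop, and nothing in the row tells the reader which.

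The outcome also depends on whether the participant agrees to further visits. If the competing visit is not attended, the premature EOT value stays in and carries a scheduled-week label.

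**Working it through.** **Inputs.** Targets and windows come from SAP Table 4. The ±7-day tolerance for scheduled visits and the assessments at each off-drug visit come from Protocol 1.3.2.

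**1. Reproduce the windows.** Midpoints between adjacent targets are (85+141)/2 = 113, (141+183)/2 = 162, (183+274)/2 = 228.5 and (274+456)/2 = 365. The windows 2–112, 113–161, 162–228 and 229–364 follow, as printed.

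**2. The comparison.** Let the EOT visit fall on day e in a window with target t, and let the scheduled visit fall on day v with |v − t| ≤ 7. If |e − t| ≥ 8, the scheduled visit is always nearer and no tie can arise. If |e − t| ≤ 7, the two visits can be combined.

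**3. Count the days, general windows.**

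| Target | Window | Days | Within ±7 | Lost to later visit | Lost to earlier visit |
|---|---|---|---|---|---|
| 85 | 2–112 | 111 | 15 | 76 | 20 |
| 141 | 113–161 | 49 | 15 | 21 | 13 |
| 183 | 162–228 | 67 | 15 | 14 | 38 |
| 274 | 229–364 | 136 | 15 | 38 | 83 |
| Total | 2–364 | 363 | 60 | 149 | 154 |

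Displaced: 149 + 154 = 303, and 303/363 = 83.5%.

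**4. DLco.** The window is 2–280 with target 183, which gives 279 days, 15 of them within ±7. Of the other 264 (94.6%), 174 lose to a later Week 26 visit and 90 to an earlier one.

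**5. Examples, taking the EOT visit 3 days after the stop.**
- Stop Day 60, EOT Day 63: 85 − 63 = 22 days from target. Off-drug vital signs at about Day 85 are used instead.
- Stop Day 105, EOT Day 108: 108 − 85 = 23 days. The Day 85 visit, before the stop, is used instead.
- Stop Day 120, EOT Day 123: 141 − 123 = 18 days. The off-drug Day 141 visit is used instead.
- Stop Day 40, EOT Day 43: the Week 26 DLco is the Day 183 value, 183 − 40 = 143 days (about 20 weeks) after the last dose. The Week 26 ABG is the Day 43 value.

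**6. Which parameters have a competing off-drug visit.**
- Vital signs: the off-drug schedule marks premature EOT and Weeks 12, 20, 26 and 39.
- DLco: premature EOT and Week 26.
- ABG: premature EOT only, and mandatory only for stops before Week 26. It is relabelled, not displaced.
- Laboratory tests: premature EOT and Weeks 20, 26 and 39. The Week 12 cell is blank as printed, so the Day 63 example cannot be asserted for haemoglobin or thyroid tests.
- Spirometry: the repeat mark falls under Week 20 as printed. The DLco count therefore carries over to FVC only if the repeat is at Week 26.

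The schedule table is damaged in the text available, so the laboratory and spirometry readings are provisional.

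**The case against.** The case against a serious reading is strong, and most of it stands.

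- **The values are not lost from safety reporting.** All laboratory and vital-sign measurements are listed. Marked laboratory abnormalities and clinically important vital signs have incidence tables (5.6.3.1, 5.6.3.2), to which displaced visits may contribute under "but they can be used for determination of clinically important endpoints". Adverse events leading to discontinuation are tabulated. This stands, and it confines the loss to by-visit descriptive statistics.
- **Dilution is not shown.** A reader might infer that washout values pull the selexipag mean toward placebo. The documents do not support this. In the general windows up to Day 364, 154 of the 303 displaced days lose to an earlier visit, which will ordinarily be on drug. The documents give no distribution of stopping times, and no shift in a mean can be calculated.
- **Including off-drug data is a stated choice.** Section 5.6 covers the entire study period, and Protocol 4.2 keeps stoppers in follow-up on the intent-to-treat principle. This stands. The defect is the missing EOT row and the unmarked mixture, not the presence of off-drug values.
- **An on-treatment limit may be intended.** The heading "Table 4 Visit Windows for double-blind treatment period" and the undefined endpoint in 5.1.1 could hint at one. If off-drug visits were outside Table 4, the 149 later displacements would vanish, but the 154 earlier ones would remain. No cut-off is written, and 5.6 points the other way.
- **Table shells were not available.** SAP 5.8.1 refers to separate output specifications, which may contain an EOT row. The assignment rule would still belong in 5.1.1.

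**Conclusion.** The point holds, and it is minor. Under the SAP as written, a premature EOT visit more than 7 days from a target day is displaced from the by-visit summaries of vital signs and DLco whenever the scheduled visit in that window is attended on time. The same applies to laboratory tests and FVC where the off-drug schedule repeats them. In the general windows this is 303 of 363 possible EOT days up to Day 364, and for DLco 264 of 279. These are shares of calendar days and say nothing about how many participants are affected. ABG keeps its premature EOT value but shows it as Week 26.

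The result assumes that the scheduled visit falls within ±7 days of target and is not combined with the EOT visit. The severity is low because efficacy is listed only, no hypothesis is tested, and the report is a synoptic one for a terminated study that the SAP describes as having very few participants (5.5.16). The displaced values can still be read individually in the listings.

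**What to change.** 1. Add an EOT / premature EOT analysis visit to Table 4 for vital signs, laboratory tests, DLco, FVC, ABG and supplemental oxygen rate. Populate it from the assessment at the EOT visit (for early stops, within 7 days after the last dose), whether or not that visit is nearest to a scheduled target.
2. Keep the by-visit rows for the entire study period, as 5.6 intends, but flag or show separately the values taken after stopping.
3. Define the endpoint time point mentioned in 5.1.1.

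Restricting the by-visit rows to last dose plus 3 days, borrowed from the adverse-event rule, would not serve. It would exclude premature EOT visits held on days 4 to 7 after the last dose, which the protocol allows, and it would override the stated analysis period.

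The cost is SAP wording, one extra row per table and one derived flag. No new data are needed.
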